**Secondary Analysis:**

- Changes in PROMIS measures (e.g., pain intensity, fatigue, and depression) will be analyzed using similar methods. Adjustments will be made for baseline values in secondary outcomes using linear regression.

**Handling Missing Data:**

- Missing data will be addressed using multiple imputation under the assumption that data are missing at random. Sensitivity analyses will compare results from imputed datasets with complete-case analyses.

**Adjustment for Covariates:**

- Analyses will adjust for baseline MME, PROMIS scores, and demographic factors (age, gender) where appropriate.

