## Study Objectives

- Primary Objective: To evaluate changes in Morphine Milligram Equivalent (MME) use from baseline to three months in patients receiving OT with or without IVR.
- Secondary Objectives:
  - To assess changes in chronic pain intensity using the Numeric Pain Rating Scale.
  - To evaluate self-efficacy, fear of movement, and functional participation using validated scales, including the Pain Self-Efficacy Questionnaire, the Tampa Scale of Kinesiophobia, and the Goal Attainment Scale.
  - To assess changes in patient-reported outcomes such as sleep disturbance, physical function, and emotional well-being using PROMIS measures.

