## Study Design & Methods

- Study Type: Interventional
- Allocation: Randomized
- Interventional Model: Parallel Assignment
- Masking: None (Open Label)
- Primary Purpose: Treatment

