**Primary Analysis:**

- Within-group changes in MME and PROMIS measures from baseline to 8 weeks will be analyzed using paired t-tests or Wilcoxon signed-rank tests (for non-normally distributed data).
- Between-group differences will be assessed using independent t-tests or Mann-Whitney U tests.

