**Challenges Due to Small Sample Size:**

- The study's small sample size (n=20) limits statistical power, increasing the risk of Type II error and reducing the ability to detect small-to-moderate effect sizes. This limitation may affect the robustness of statistical inferences. Findings should be interpreted with caution and viewed as exploratory in nature.

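### The covariate set for each outcome is left open in an open-label trial of 20 patients; fixing it at the outcome's own baseline value would settle the model and protect precision.

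*Combined protocol and SAP*

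**What the plan says.** Three paragraphs of the Statistical Considerations bear on the between-arm model.

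- **Primary Analysis:** "Between-group differences will be assessed using independent t-tests or Mann-Whitney U tests". Neither test takes a covariate.
- **Secondary Analysis:** "Adjustments will be made for baseline values in secondary outcomes using linear regression". This is the only adjusted model the plan names, and it is named for secondary outcomes.
- **Adjustment for Covariates:** "Analyses will adjust for baseline MME, PROMIS scores, and demographic factors (age, gender) where appropriate". PROMIS scores are plural, with no number and no domains, and the closing qualifier has no criterion attached.

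The paragraph on sample size says "The study's small sample size (n=20) limits statistical power, increasing the risk of Type II error" and calls the findings exploratory. It does not connect the sample size with the number of covariates. Study Design & Methods gives "Allocation: Randomized" without a ratio, and no masking.

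**The concern.** The three paragraphs do not add up to one model. For MME, the analyst could report an unadjusted test, a regression on baseline MME, or a regression that adds age, gender and some PROMIS scores. Each PROMIS outcome has the same freedom. Nothing says the choice is made before outcome data are seen, and the trial is open label, so whoever makes it may know the allocation.

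The choice also affects precision. In a randomised comparison of 20 patients, a covariate that does not predict the outcome uses a residual degree of freedom and adds variance through chance imbalance. The outcome's own baseline usually repays that cost. Whether further covariates do so depends on how much they explain beyond it, and the document offers no evidence on this.

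**Working it through.** The plan has no figure to reproduce: n=20 comes with no effect size, SD, alpha or power.

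**Inputs from the document.** N = 20. The number of covariates k depends on how the covariate paragraph is read:

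- k = 3: the outcome's own baseline, age and gender.
- k = 4: as above, plus baseline MME for a PROMIS outcome, or one PROMIS score for MME.
- k = 6: baseline MME, age, gender and three PROMIS scores, for example those in "Changes in PROMIS measures (e.g., pain intensity, fatigue, and depression) will be analyzed using similar methods".
- k = 9: as for k = 6, plus the three domains in the objectives, "sleep disturbance, physical function, and emotional well-being using PROMIS measures". This is an upper reading. It pools two illustrative lists of outcomes, and it would be 8 if emotional well-being and depression are one score.

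**Assumptions.** 20 is the total; allocation is 1:1; intervals are two-sided 95%; covariates are roughly normal (an approximation for gender).

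**Step 1: k covariates against own baseline only.** The variance factor for k covariates is (N−3)/(N−3−k), on N−2−k residual df. If the extra covariates explain nothing, the width ratio to the k = 1 model is

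√[(N−4)/(N−3−k)] × t(0.975, N−2−k) / t(0.975, N−3).

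The share of the variance left after baseline that the extras must explain to break even is 1 − 1/ratio². At N = 20 the k = 1 model has 17 df and t = 2.1098.

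| k | residual df | t | calculation | CI width ratio | break-even share |
|---|---|---|---|---|---|
| 3 | 15 | 2.1314 | √(16/14) × 2.1314/2.1098 | 1.08 | 14% |
| 4 | 14 | 2.1448 | √(16/13) × 2.1448/2.1098 | 1.13 | 21% |
| 6 | 12 | 2.1788 | √(16/11) × 2.1788/2.1098 | 1.25 | 36% |
| 9 | 9 | 2.2622 | √(16/8) × 2.2622/2.1098 | 1.52 | 57% |

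With baseline in the model, the arm estimate is the same whether the response is follow-up or change, so these ratios do not depend on that choice.

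**Step 2: sensitivity to N.** If 20 is per arm (N = 40), k = 4 gives √(36/33) × 2.0322/2.0262 = 1.05. If 16 of 20 patients are analysed (an assumed loss), k = 4 gives √(12/9) × 2.2281/2.1604 = 1.19, with break-even at about 30%.

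**Step 3: against the unadjusted tests actually planned.** Here

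ratio² = (1−R²) × (N−3)/(N−3−k) × [t(0.975, N−2−k) / t(0.975, N−2)]²,

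where R² is the share of outcome variance explained by all k covariates. At N = 20 and R² = 0 the ratio is 1.04 (k = 1), 1.17 (k = 4) and 1.57 (k = 9). Break-even R² is 0.07, 0.27 and 0.59.

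Suppose only the outcome's baseline is prognostic, with baseline–follow-up correlation r and equal SDs. Then R² = (1−r)/2 for a change score and r² for a follow-up score.

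| Benchmark | r | k = 1 | k = 4 |
|---|---|---|---|
| change-score t-test | 0.5 | 0.90 | 1.01 |
| change-score t-test | 0.7 | 0.95 | 1.08 |
| change-score t-test | 0.8 | 0.98 | 1.11 |
| follow-up-score t-test | 0.5 | 0.90 | 1.01 |
| follow-up-score t-test | 0.7 | 0.74 | 0.83 |

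A simulation of Step 3 (N = 20, 10 per arm, 4,000 runs per setting) gave mean width ratios within about 5% of the formula.

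**The case against.** A reader might infer that the list is simply too long for 20 patients, so that the planned adjustment will widen the interval. The document does not support that. It gives no R² and no count of PROMIS scores, and its qualifier commits no model to the whole list. With four covariates, 14 residual df remain, and the interval is narrower than the unadjusted one once R² exceeds about 0.27. At r = 0.7 against a follow-up-score comparison, it is 17% narrower.

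Nor does the plan say that nine covariates will be fitted. That count comes from combining examples of outcomes. A respective reading (baseline MME for MME, the PROMIS baseline for PROMIS, plus age and gender) gives three, and fewer are allowed.

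A reader might also see a contradiction between the secondary-analysis and covariate paragraphs. The former does not say that baseline is the sole covariate, so the latter may be adding to it. The two are unreconciled, not shown to conflict.

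Finally, age and gender are conventional adjusters, and the plan already admits low power and calls its findings exploratory. That lowers the stakes but does not settle which model is reported. What stands after all this is that the set is open, and that covariates beyond the outcome's baseline have a measurable price.

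**Conclusion.** The point holds as one of under-specification with a precision cost attached. On the shorter readings the cost is modest: an interval about 8–13% wider than with own-baseline adjustment if the extra covariates are uninformative. It becomes substantial, about 25–52%, only if several PROMIS scores enter one model, and the top of that range rests on a reading the plan does not state. The figures assume 20 patients in total, allocated 1:1. No general claim that adjustment widens the interval relative to the planned unadjusted tests can be made, because the direction depends on correlations that are not given. The change is worth making because it is cheap and removes an analytic choice from an unmasked trial.

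**What to change.** State in the Primary Analysis, Secondary Analysis and Adjustment for Covariates paragraphs that every between-arm comparison, including MME, uses one linear model containing arm and the baseline value of that outcome as the only covariate. Move age, gender and all other baseline scores to a single labelled sensitivity model with its covariates listed. These variables may still serve as auxiliary variables in the multiple imputation.

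The cost is a few sentences of SAP text. The statistical downside is that any gain from a strongly prognostic extra covariate is given up in the main model. At four covariates in total, the three extras would have to explain more than about 21% of the variance left after baseline before that became a net loss.

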**Challenges Due to Small Sample Size:**

- The study's small sample size (n=20) limits statistical power, increasing the risk of Type II error and reducing the ability to detect small-to-moderate effect sizes. This limitation may affect the robustness of statistical inferences. Findings should be interpreted with caution and viewed as exploratory in nature.

**Software:**

- All statistical analyses will be performed using R (version 4.3.1). Detailed analysis scripts will be maintained to ensure reproducibility.

**Subgroup and Sensitivity Analyses:**

- Subgroup analyses will examine treatment adherence and baseline PROMIS scores. Sensitivity analyses will explore the impact of different imputation methods for missing data.

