### Arms and Interventions:

1. Active Comparator: Occupational Therapy (OT)
  - Participants receive six 1-hour outpatient OT sessions tailored to chronic pain management, including education, exercises, stress management, and daily activity planning.
2. Experimental: Occupational Therapy + Virtual Reality (OT+VR)
  - Participants receive a combination of OT and 10–30 minutes of IVR during each session. IVR sessions include interactive exercises and games, followed by therapist-led debriefing.

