### Measurements:

- Participants complete surveys before and after each therapy session.
- Additional bi-weekly online surveys are administered for the study duration.

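### Treatment adherence, observed only after randomisation, is listed as a subgroup factor; outcome comparisons by adherence would not be protected by randomisation (minor, interpretability)

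*Combined protocol and SAP*

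**What the plan says.** Under Subgroup and Sensitivity Analyses the plan states: "Subgroup analyses will examine treatment adherence and baseline PROMIS scores". Nothing more is said about subgroups. Adherence is not defined, no cut-off or outcome is named, and the comparison is not stated.

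Other sections that bear on this:

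- Study Design & Methods: "Allocation: Randomized", parallel arms, open label.
- Arms and Interventions: in the control arm, "Participants receive six 1-hour outpatient OT sessions tailored to chronic pain management". The experimental arm adds immersive VR and a debriefing to the sessions. Adherence therefore refers to something delivered after allocation, with different content in each arm.
- Primary Analysis: "Between-group differences will be assessed using independent t-tests or Mann-Whitney U tests". The within-group tests compare participants with their own baseline.
- Adjustment for Covariates: "Analyses will adjust for baseline MME, PROMIS scores, and demographic factors (age, gender) where appropriate".
- Challenges Due to Small Sample Size: "Findings should be interpreted with caution and viewed as exploratory in nature". The reasons given there are power and Type II error.

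**The concern.** The sentence puts two different kinds of variable side by side. A baseline score cannot be affected by the arm, so the arms remain a randomised comparison within each of its levels. Adherence can be affected by the arm. Participants know what they were allocated to, and the sessions they are asked to attend differ. Those who adhere to OT plus VR may differ in prognosis from those who adhere to OT alone.

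Two outcome contrasts would fit the sentence:

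1. OT+VR versus OT within adherence strata. This conditions on a post-randomisation variable.
2. Adherers versus non-adherers. These groups were never randomised against each other.

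What is at stake is how a result may be read. A difference in either contrast could not be taken as an effect of VR or of adherence, and the plan does not say so. More participants would narrow the interval but would not remove this problem.

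**Working it through.** The plan gives no figure to reproduce: it states n=20, but no significance level, effect size, SD or expected adherence. The structural point follows from the sections above. The arithmetic below only shows what sizes are possible.

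**Assumptions, none from the documents except n=20.** 20 is the total, split 10 per arm; no true treatment effect; outcome in SD units; two-sided 5% level. A participant adheres when a standard normal latent variable exceeds c = Φ⁻¹(1−p), where p is the adherence rate. The latent variable has correlation r with outcome.

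**Formulas.** Mean outcome in adherers = r·φ(c)/p. Mean outcome in non-adherers = −r·φ(c)/(1−p).

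- p = 0.6: φ(c) = 0.386, so the multipliers are 0.644 (adherers) and −0.966 (non-adherers).
- p = 0.7: φ(c) = 0.348, so they are 0.497 and −1.159.

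**Contrast 1, between arms within a stratum**

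| Case | Adherers | Non-adherers |
|---|---|---|
| Same rate and same r in both arms | 0 | 0 |
| 60% vs 70%, r = 0.3 in both | 0.3 × (0.644 − 0.497) = 0.04 | 0.3 × (1.159 − 0.966) = 0.06 |
| 60% vs 70%, r = 0.5 in both | 0.5 × 0.147 = 0.07 | 0.5 × 0.193 = 0.10 |
| 60% in both, r = 0.5 vs 0 | 0.5 × 0.644 = 0.32 | 0.5 × 0.966 = 0.48 (absolute) |
| 60% in both, r = 0.6 vs 0 | 0.6 × 0.644 = 0.39 | 0.6 × 0.966 = 0.58 (absolute) |

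With 6 and 7 adherers, the 60% versus 70% cases give rejection rates of 5.1% to 5.2% (noncentral t), practically nominal. The last row gives 9.3% with 6 adherers per arm. Nothing in the documents points to the last two rows; they show that the result depends on the adherence mechanism, and that non-adherers can be affected more than adherers.

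**Effect of covariate adjustment.** In a simulation of the 60% versus 70% case, a baseline covariate carrying half of the adherence–outcome link left 0.02 to 0.04 SD in adherers after adjustment. A covariate carrying all of the link left about 0, and one carrying none changed nothing. Adjustment removes only the selection that runs through the listed variables.

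**Contrast 2, adherers minus non-adherers within an arm.** Difference = r·φ(c)/[p(1−p)]. At p = 0.6 this is 0.386/0.24 = 1.61 times r.

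- r = 0.3: 0.48 SD; r = 0.5: 0.80 SD, with no effect of adherence at all.
- Rejection with 6 versus 4 participants: 10.2% and 19.6% at a nominal 5%. Simulated arms of 10 gave 9.5% and 19.1%.
- If adherence is unrelated to prognosis, the difference is 0. An identical mechanism in the two arms does not help here.

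**Precision (95% half-width)**

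- 6 versus 6: 2.228 × √(1/6 + 1/6) = 1.29 SD.
- 6 versus 4: 2.306 × √(1/6 + 1/4) = 1.49 SD.

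In every case shown the half-width exceeds the bias.

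**The case against.** The strongest case against is that little follows from this. The sentence makes no causal claim, the plan calls its findings exploratory without excepting subgroups, and in the mildest between-arm cases the bias is negligible. All of that stands, and it is why the point is minor. What it leaves open is the reason for caution: the caveat rests on sample size and does not tell a reader that this contrast is non-randomised.

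A second objection is that examining adherence could simply mean reporting it by arm, which randomisation would protect. That is possible. It is a strained reading of a subgroup analysis listed beside a baseline score, and the fix preserves it.

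Third, the plan does not announce an adherer versus non-adherer test. Its within-group tests, "Within-group changes in MME and PROMIS measures from baseline to 8 weeks will be analyzed using paired t-tests" or the signed-rank equivalent, are against own baseline. This also stands: the 0.48 to 0.80 SD figures describe a contrast that the sentence permits, not one that the plan specifies.

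Fourth, the baseline PROMIS subgroup is also under-specified, with no domain, cut-point or interaction test. That is true, but it is a separate matter; as a pre-treatment factor it does not share the defect described here.

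**Conclusion.** The point holds as a cheap improvement of minor severity. Adherence is a post-randomisation variable listed as a subgroup factor, and any comparison of outcomes by adherence, between or within arms, lacks the protection of randomisation.

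Three stronger conclusions might be inferred, and the documents support none of them:

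- That such contrasts must be biased. The between-arm contrast is unbiased if the adherence mechanism is the same in both arms, and the within-arm contrast if adherence is unrelated to prognosis. The documents do not support either assumption, but they do not refute them. Size and direction cannot be derived.
- That the trial's main result is compromised. The primary analysis does not condition on adherence.
- That the plan intends to claim an effect in adherers. It states no contrast and no claim.

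The illustrative sizes rest on assumed adherence rates and correlations and on 10 participants per arm. They run from 0 to 0.07 SD in adherers between arms (0 to 0.10 SD in non-adherers) when both arms share one correlation of at most 0.5 and adherence differs by at most 60% versus 70%. They rise to 0.58 SD when the correlation differs sharply between arms, and to 0.48 to 0.80 SD for adherers against non-adherers.

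**What to change.** Replace the first sentence of Subgroup and Sensitivity Analyses with text along these lines:

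> Subgroup analyses will use baseline PROMIS scores and are exploratory. Adherence (sessions attended, where recorded) will be described by arm. Any comparison of outcomes by adherence, between or within arms, will be reported as descriptive, non-randomised and non-causal, and not as a treatment effect.

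The same label applies to both contrasts, so neither is banned while the other is allowed.

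The cost is a short text change. The loss is an adherer-only p-value that could be claimed as a treatment effect. Attendance may be countable from the session surveys, since "Participants complete surveys before and after each therapy session". A missed survey is not a missed session, however, so attendance must be taken from session records if the surveys are incomplete. The documents do not say that minutes of VR use are recorded, so the text does not rely on them.
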